6.2. Safety Endpoints

Co-Primary

- *Malignancies, excluding non-melanoma skin cancers (adjudicated).*
- *Major adverse cardiovascular events (MACE) (adjudicated).*

The definitions of MACE used in this study are consistent with those outlined in the Standardized Definitions for Cardiovascular and Stroke End Point Events in Clinical Trials¹ with the exclusion of cardiovascular death due to pulmonary embolism. The following events are included, as defined:

- *Cardiovascular death:*
 - *Death due to acute myocardial infarction (MI);*
 - *Sudden cardiac death;*

- *Death due to heart failure;*
- *Death due to stroke;*
- *Death due to cardiovascular procedures;*
- *Death due to cardiovascular hemorrhage;*
- *Death due to other cardiovascular causes: peripheral artery disease.*
- *Non-fatal myocardial infarction (MI).*
- *Non-fatal stroke of any classification, including reversible focal neurologic defects with imaging evidence of a new cerebral lesion consistent with ischemia or hemorrhage.*

Secondary

- *Opportunistic infection events including tuberculosis (adjudicated):*
 - The opportunistic infection (OI) events by all OIs, tuberculosis adjudicated as OI, herpes zoster adjudicated as OI and all other OI;
 - Tuberculosis events separately from the evaluation of opportunistic infections:
 - Proportion of subjects with QuantiFERON-TB Gold (QFT) or Tuberculin Skin Test (TST) positive subjects with a history of TB by region;
 - QFT and TST newly positive by time in the study, newly positive treated with Isoniazid (INH) or other Tuberculosis (TB) prophylaxis, newly positive with positive Chest X-Ray (CXR), newly positive with negative CXR by region;
 - Patient Years exposure by treatment arm, with or without TB;
 - Proportion and Incidence Rate of Tuberculosis by time in the study;
 - Tuberculosis Severity and Seriousness by treatment arm.
- *Hepatic events (adjudicated) including:*
 - Drug-induced Liver Injury (DILI) - Probable, Highly Likely and Definite;
 - DILI – Listed separately;
 - DILI – Cases meeting classification and severity;
 - Subjects with elevations of Transaminase levels >1x Upper Limit of Normal (ULN), ≥3xULN, ≥5xULN (based on laboratory values).

- *Cardiovascular events other than MACE (adjudicated).*
- *All Adverse Events (AEs), including Serious Adverse Events (SAEs):*
 - Herpes zoster:
 - Baseline Characteristics with and without herpes zoster;
 - Patient Years of exposure with and without herpes zoster;
 - Proportion and Incidence Rate by Age Category, Time in study for all Herpes Zoster;
 - Proportion and Incidence Rate by Age Category and Time in Study for Herpes zoster by number of dermatomes;
 - List of subjects with Herpes Zoster Ophthalmic and Visceral cases;
 - List of subjects with serious Herpes Zoster with and without history of chicken pox (varicella); with and without history of chicken pox (varicella) vaccine; with and without history of herpes zoster vaccine (varicella); with and without history of history of shingles (herpes zoster);
 - List of subjects with non-serious Herpes Zoster with and without history of chicken pox (varicella); with and without history of chicken pox vaccine (varicella); with and without history of herpes zoster vaccine (varicella); with and without history of shingles (herpes zoster);
 - Risk factors associated with herpes zoster (cox regression analysis) including region, baseline corticosteroid use, age group, smoking status, treatment arm;
 - Time to resolution of all Herpes Zoster Cases, single dermatomes, 2 adjacent dermatomes, disseminated herpes zoster by treatment arm;
 - Severity and seriousness of Herpes Zoster by treatment arm;
 - Post Herpetic neuralgia after Herpes Zoster by treatment arm;
 - Permanent and temporary discontinuations due to Herpes Zoster by treatment arm;
 - Herpes Zoster considered OI by treatment arm.
 - Serious infections.
 - Gastrointestinal (GI) perforations (adjudicated):

- Incidence rate for all GI events adjudicated as meeting criteria by treatment arm;
- Listing of all GI events adjudicated, including location, risk factors and outcome, by treatment arm.

- Nonmelanoma skin cancers (adjudicated).
- Interstitial lung disease (adjudicated by a sponsor review committee, independent of the study team).
- Deep vein thrombosis (DVT) (adjudicated): subjects who experienced any DVT.
- Pulmonary embolism (PE) (adjudicated): subjects who experienced any PE.
- Arterial thromboembolism (ATE) (Standardized MedDRA Query (SMQ)): subjects who experienced any ATE.
- DVT or PE (adjudicated): subjects who experienced any DVT or PE.
- Thromboembolic events (TE) subjects who experienced any DVT (adjudicated), PE (adjudicated) or ATE (SMQ).
- SMQ of Hypertension.

- *Clinically significant abnormal laboratory parameters:*
 - Hematology, including hemoglobin, neutrophils and lymphocytes;
 - Lipids;
 - Liver tests including Alanine Aminotransferase (ALT), Aspartate Transaminase (AST) and total bilirubin.

- *All-cause mortality (adjudicated)* (also known as all-cause deaths associated with the adjudicated primary endpoint criteria under Bullet Deaths below).

- *Reasons for permanent or temporary discontinuation of study medication.*

- *Concomitant drugs by treatment group, in the following categories:*
 - *Lipid Lowering Agents (LLA) including Statins;*
 - *DMARDS;*
 - *Steroids;*
 - *Analgesics and Nonsteroidal Anti-inflammatory Drug (NSAIDS);*

- *INH and Rifampacin.*
- *Laboratory Data Descriptive Statistics for the following tests:*
 - *Hemoglobin;*
 - *Platelets;*
 - *Creatine Kinase;*
 - *Serum Creatinine;*
 - *Total Cholesterol;*
 - *Low Density Lipoprotein Cholesterol (LDL-c);*
 - *High Density Lipoprotein Cholesterol (HDL-c);*
 - *Total Cholesterol/HDL-c Ratio;*
 - *Total Cholesterol/LDL-c Ratio;*
 - *Triglycerides.*
- *Vital Sign Descriptive Statistics Summaries, including BMI.*
- *Baseline Characteristics including:*
 - *Duration of Rheumatoid Arthritis (RA);*
 - *Cardiovascular Risk;*
 - *Subjects with Nodules, Sjogren's Syndrome, Anemia of Chronic Disease, Pulmonary manifestations;*
 - *Joints (JTS), CDAI, SDAI, Smoking History, Alcohol use.*
- *Deaths:*
 - *List of all-cause deaths associated with the adjudicated primary endpoint criteria;*
 - *List of all-cause deaths;*
 - *Incidence rate (95% CI) for all-cause deaths associated with the adjudicated primary endpoint criteria;*
 - *Incidence rate (95% CI) for all-cause deaths.*

- Patient Years exposure by treatment arm, including standard of care and by time point.

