This Post-Authorization Safety Study (PASS) was developed in response to the requirements of the US Food and Drug Administration to further define the safety profile of tofacitinib 5 mg BID and 10 mg BID, especially with respect to major adverse cardiovascular events (MACE) and malignancies, and to provide comparative safety analyses to a TNF inhibitor in an open-label manner.

The subcutaneously self-administered TNFi's, adalimumab and etanercept, will be included in this study. Subjects randomized to receive TNFi in the United States (US), Puerto Rico and Canada will receive adalimumab; in all other countries, subjects randomized to receive TNFi will receive etanercept.

Based on the totality of the non-clinical and clinical data generated thus far, identified risks associated with tofacitinib include infection, lipid elevations, anemia, neutropenia and malignancies. The identified risks for the completed studies with tofacitinib in RA are presented in the XELJANZ™ (tofacitinib citrate) Investigator Brochure.

New safety information about tofacitinib was provided to Study A3921133 investigators on 19 February 2019. That information stated that Pfizer received communication from the Tofacitinib Rheumatology Data Safety Monitoring Board (DSMB) stating that on the basis of the data reviewed thus far in Study A3921133, there is a statistically and clinically important difference in the occurrence of pulmonary embolism within the tofacitinib 10 mg BID treatment arm compared to the TNFi control arm, and the overall incidence per person year in the tofacitinib 10 mg BID arm is substantially higher than the TNFi control arm and substantially higher than observed in other studies across the tofacitinib program. Additionally, the DSMB noted an increase in all-cause mortality in the 10 mg BID arm compared to the tofacitinib 5 mg BID and TNFi treatment arms.

Based on the totality of evidence including a review of selected efficacy parameters and a finding of only minor increments in efficacy with tofacitinib 10 mg BID beyond the efficacy seen in the 5 mg BID group, the DSMB further stated that continued treatment with tofacitinib 10 mg BID in Study A3921133 entails a risk that is not sufficiently balanced.

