2.2.1.2. Secondary Safety Endpoints

The secondary safety endpoints will include an evaluation of the following events:

- Opportunistic infection events including tuberculosis (adjudicated).
- Hepatic events (adjudicated).
- Cardiovascular events other than MACE (adjudicated).
- All adverse events (AEs), including serious adverse events (SAEs).
- Clinically significant abnormal laboratory parameters.
- All cause mortality (adjudicated).
- Reasons for permanent or temporary discontinuation of study medication.

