9.7.3. Cardiovascular Safety Endpoint Adjudication Committee

The Cardiovascular Endpoint Adjudication Committee (CV-EAC) will evaluate and adjudicate selected CV safety events by a consistent set of criteria. Case review and assessment by the CV-EAC will be independent of Pfizer.

Events will be identified for adjudication by study investigators, Pfizer personnel (or designee) and/or by search of the clinical and safety databases. Cardiovascular events to be adjudicated include:

- Death (coronary and non-coronary).
- Myocardial Infarction.
- All Coronary Revascularization.
- Unstable Angina.
- New Ischemic Heart Disease.
- Stroke (fatal and non-fatal).
- Transient Ischemic Attack (TIA).
- Congestive Heart Failure (CHF).
- Peripheral Arterial Vascular Disease (PAVD) – first diagnosis or procedure.
- Deep Vein Thrombosis
- Pulmonary Embolism
- Arterial Embolism
- Arterial Thrombosis

The process of adjudication will be defined in the Cardiovascular Endpoint Adjudication Committee's charter.

Both the reported and adjudicated event terms will be reported in the study database; analyses will be based on adjudicated events.

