		
 5. Added Section 7.1.1 specified the rules of counting the time to event, the text was removed from Section 5.3 (Safety Analysis Set) to Section 7.1.1. 6. Section 7: specified that no imputation will be done for safety endpoints, and no imputation will be done for efficacy endpoints after the declared study completion day. 7. Section 8: specified that data collected after subject’s discontinuation from the study will be summarized separately from the analyses described in this SAP. 8. Section 8.2: clarified that all analyses identified for the tofacitinib 10 mg BID treatment arm will be conducted as stated prior to protocol amendment 8. 9. Section 8.2.2: clarified how data collected under standard of care will be summarized for TEAE. 10. Section 8.2.2: removed 3-tier analysis of AEs. 11. Section 8.2.2: added TEAE definition. 12. Section 8.2.2: added endpoint of DVT, PE, ATE, DVT or PE to analysis. 13. Section 8.2.5: added for additional non-standard safety table details. 14. Appendix 1.1: added rules of visit windowing specific to SF-36, EQ-5D, and WPAI due to their different schedule of evaluations, as well as those specific to lipids (fasting) due to the same reason.
Amendment 3 (SAP version 4)	30-Jun-2020	
 1. Section 5: clarified FAS and SAS. 2. Section 6.2: added the word “adjudicated” for the adjudicated safety endpoints for clarity and internal consistency within the document. Clarified terminology for deaths (updated terms to: all-cause deaths and all-cause deaths associated with adjudicated primary endpoint criteria) for clarity and internal consistency within the document. 3. Section 7.2: for continuous endpoints, updated missing data handling by use of a MMRM for consistency with Sponsor’s convention established across tofacitinib development programs. 4. Section 7.3: added a new section to describe missing data handling due to COVID-19 pandemic and associated summaries and data listings. 5. Section 8.1.2: exact 95% CI will be used instead of approximate 95% CI for the crude incidence rate for consistency with Sponsor’s convention established across tofacitinib development

Document	Version Date	Summary of Changes

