8.2.2. Analyses of Other Safety Endpoints

The analyses will be based on the Safety Analysis Set. The 28-Day On-Treatment Time will be applied to all the events of interest, see [Section 7.1.1](#).

The times to the secondary endpoints of opportunistic infection events excluding tuberculosis, tuberculosis, hepatic events, cardiovascular events (MACE and others), serious infections, GI perforations, non-melanoma skin cancers, interstitial lung disease, DVT, PE, ATE, DVT or PE, thromboembolic events (TE) and all-cause mortality will be analyzed by Cox models via univariate model analysis. See [Section 8.1.1](#). The 28-Day On-Treatment Time analysis will be conducted.

The times to herpes zoster events will be analyzed by a multivariate Cox model with region, baseline corticosteroid use, age group, smoking status, treatment as predictors. The 28-Day On-Treatment Time analysis will be conducted.

Unadjusted, or “crude” incidence rates will be calculated as well. Note that the ratios of these rates approximate, but are not exactly equal to, the hazard ratios.

A Surveillance, Epidemiology, and End Results (SEER) analysis of the malignancy endpoint will be conducted. In this analysis, standardized incidence ratio (SIR) for malignancies represents the ratio of the incident number of cases of cancer in the tofacitinib population to the incident number that would be expected if the study population had the same incidence rate as the US population. By way of interpretation, a SIR of more than 1.0 indicates that proportionally more cases of cancer have occurred in the tofacitinib population than the comparator, whereas a SIR of less than 1.0 indicates that proportionally fewer cancer cases have occurred.

The Sponsor has standard (ie, used for all its clinical trials) summary displays and listings for MedDRA-coded adverse events, demography, medical history, length of time in study and discontinuation, concomitant and concurrent medications, physical examination, ECG, laboratory tests, weight, pulse rate, and blood pressure. These standards, called *CaPS (CDISC and Pfizer Standards)*, will be utilized in the reporting of these routine safety variables. For laboratory tests total cholesterol, LDL-c, HDL-c, total cholesterol/HDL-c ratio, LDL-c/HDL-c ratio, Triglyceride, the summary will be produced by subjects on statins, subjects not on statins and subjects on any lower lipid agents including statins.

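### SAP 6.2 ties all-cause mortality to an undefined subset of deaths, so the mortality Cox model, read literally, can omit deaths in subjects without adjudicated MACE or malignancy

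*SAP*

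**What the plan says.** Protocol 2.2.1.2 and 9.2.2 list all-cause mortality, marked as adjudicated, among the secondary safety endpoints. Neither section limits it to particular causes.

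SAP 6.2 repeats the item and adds that it is "also known as all-cause deaths associated with the adjudicated primary endpoint criteria under Bullet Deaths below". The Deaths item further down the same section has four entries: a listing and an incidence rate for that group, and a separate listing and a separate "Incidence rate (95% CI) for all-cause deaths". The phrase that marks off the first group is not defined anywhere in the SAP.

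SAP 8.2.2 gives the between-arm model. After a series of other endpoints it ends: "thromboembolic events (TE) and all-cause mortality will be analyzed by Cox models via univariate model analysis". On time at risk it says: "The 28-Day On-Treatment Time will be applied to all the events of interest". Protocol 9.2.2 plans both ITT and on-treatment analyses for the secondary endpoints other than adverse events and laboratory abnormalities, and mortality is one of these.

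**The concern.** A label that says all causes has been attached to a group that, by the SAP's own layout, is not all deaths. An analyst who follows 6.2 into 8.2.2 would fit the mortality Cox model to the smaller group and report it as all-cause mortality. Another analyst, reading 8.2.2 on its own, would use every death. The SAP does not settle which is right.

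The deaths at risk of omission are relevant to the trial's main safety signal. Protocol 1.2 reports a statistically and clinically important PE difference for 10 mg BID against TNFi, and adds that "the DSMB noted an increase in all-cause mortality in the 10 mg BID arm compared to the tofacitinib 5 mg BID and TNFi treatment arms". PE death is excluded from MACE by definition, and a fatal infection is neither MACE nor malignancy. A mortality hazard ratio limited to primary-endpoint deaths would be a poor guide to that signal, and its label would hide the limitation.

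**Working it through.** The plan states no event target, margin or power for mortality, so there is no figure to reproduce. The check is a comparison of texts.

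1. **What adjudicated means in the protocol.** Section 9.7.3 sends both coronary and non-coronary deaths to the cardiovascular committee. Section 8.6.1 names non-cardiovascular deaths among the events that need adjudication and sets them apart from the co-primary endpoints. The word therefore describes review of the death. It does not mean that the death met a primary criterion.

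2. **Whether the protocol overrides the SAP.** Protocol section 9 lets the SAP modify the planned analyses and requires an amendment only for major changes to the primary endpoint or its analysis. The unrestricted protocol wording does not by itself cure the SAP definition.

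3. **Whether the two SAP groups differ.** If they were the same, two listings and two incidence rates would be redundant. The SAP amendment log, used here only as evidence of intent, records the two as distinct terms: "updated terms to: all-cause deaths and all-cause deaths associated with adjudicated primary endpoint criteria".

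4. **What the restricted group could contain.** The primary criteria are MACE without PE death, and malignancy excluding non-melanoma skin cancer. The undefined link has at least two readings: (a) the death itself meets a primary criterion; (b) the subject had an adjudicated primary event and died of any cause.

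| Death | Reading (a) | Reading (b) |
|---|---|---|
| PE or infection, no adjudicated primary event | out | out |
| PE or infection, adjudicated primary event earlier | out | in |
| Fatal MI, stroke or malignancy | in | in |

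The first row is omitted on either reading.

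5. **Whether the Cox model inherits the restriction.** SAP 8.2.2 introduces its series as secondary endpoints. In the SAP text the term all-cause mortality occurs only there and in 6.2; elsewhere the SAP speaks of deaths. The natural antecedent is the 6.2 endpoint. Against that, 8.2.2 omits the word adjudicated and gives no cross-reference to either group.

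6. **Time at risk.** Under SAP 7.1.1 the 28-day analysis censors a subject who switches to standard of care no later than 28 days after the last dose of randomized drug. Deaths after that point do not count. SAP 8.2.2 has no Total Time mortality analysis to match the ITT analysis in Protocol 9.2.2.

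7. **Illustration, all inputs assumed.** Let the hazard ratio for deaths inside the restricted group be 1.0, let s be the share of control-arm deaths outside it, and let h be the hazard ratio for those deaths. The restricted hazard ratio is then 1.0 by construction, and the hazard ratio for all deaths is about (1 − s) + s × h.

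| h | s = 0.3 | s = 0.5 | s = 0.7 |
|---|---|---|---|
| 1.5 | 1.15 | 1.25 | 1.35 |
| 2.0 | 1.30 | 1.50 | 1.70 |
| 3.0 | 1.60 | 2.00 | 2.40 |

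For example, h = 2.0 and s = 0.5 give 0.5 + 0.5 × 2.0 = 1.50. If the same share s is omitted in both arms, the standard error of the log hazard ratio grows by 1/√(1 − s): 1.20, 1.41 and 1.83 for s = 0.3, 0.5 and 0.7.

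**The case against.** A reader might infer that PE deaths, infection deaths and all other deaths outside the primary endpoints are definitely removed from the only mortality comparison in the plan, and that an excess of them could not be seen. The documents do not support that, for four reasons.

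- SAP 8.2.2 says only all-cause mortality, which in plain words means death from any cause. That the model takes on the 6.2 restriction is an inference, though the natural one.
- The restricting phrase is undefined. On reading (b), a fatal PE or infection in a subject with an adjudicated malignancy or MACE would still count.
- All deaths remain in the reporting. SAP 6.2 plans a listing and an incidence rate with 95% CI, SAP 8.1.2 gives the exact method for that interval, and SAP 8.2.5 includes all deaths in the age-subgroup analysis, although without a stated method. PE, DVT or PE, serious infections and opportunistic infections have their own Cox models, and a fatal PE counts as a PE event. An excess would show in the crude rates.
- The mortality Cox model in 8.2.2 is the only one in the SAP's main analysis. In the two documents together it is not the only one planned, because Protocol 9.2.2 also promises an ITT analysis.

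It is also fair to say that no decision rule depends on mortality: SAP 4.2 uses only MACE and malignancy. The illustration shows what could happen under its assumptions and is not a forecast.

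These points limit the consequence but leave the defect. The definition in 6.2 contradicts the protocol endpoint and its own label. Crude rates, and models that pool fatal with non-fatal events, do not replace a correctly defined mortality hazard ratio.

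**Conclusion.** The point holds as a contradiction in an endpoint definition. SAP 6.2 equates the protocol's unrestricted mortality endpoint with an undefined group that the same section separates from all-cause deaths. Taken literally, this carries into the Cox model in 8.2.2 and leaves out at least the deaths of subjects who had neither adjudicated MACE nor adjudicated malignancy. Total exclusion of PE and infection deaths is not established, and nothing suggests that such deaths would go unreported.

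The size cannot be stated, because the documents contain no death counts or causes of death. Over the assumed ranges (s from 0.3 to 0.7, h from 1.5 to 3.0), a restricted hazard ratio of 1.0 could stand beside a ratio of 1.15 to 2.4 for all deaths. That range rests wholly on placing the excess outside the restricted group. The co-primary conclusions are unaffected.

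**What to change.** - In SAP 6.2, delete the statement that the endpoint is also known by the restricted name. Define all-cause mortality as death from any cause and carry the adjudicated cause as a descriptor.
- In SAP 8.2.2, state that the mortality Cox model uses that endpoint.
- Rename the subset, for example deaths meeting adjudicated MACE or malignancy criteria. Say whether it goes by cause of death or by any earlier primary event, and keep it as a supportive display.
- Add a Total Time (ITT) mortality analysis beside the 28-day on-treatment analysis, so that the SAP matches Protocol 9.2.2.

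The cost is a few sentences in SAP 6.2 and 8.2.2 and one further run of a model already specified. Deaths are already recorded and adjudicated, so no new data are needed.

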6.3. Other Endpoints

6.3.1. Pharmacokinetics Endpoints

None.

6.3.2. Pharmacodynamics Endpoints

None.

